Each CHW will collaborate with church leaders (see study sites and letters of support) to organize depression screening events at church health-focused programs. Two CHWs and at least one Project Coordinator (PC) will be present at the church for each screening event to assist with scoring the Patient Health Questionnaire-9 (PHQ-9), interpreting the results, and study enrollment. Eligibility for depression screening include: 1) Adults 18 years and older; and 2) English-speaking. There are no exclusion criteria for general depression screening. The screening will occur in a private space in the church to protect participant confidentiality. The screening survey will include the PHQ-9 and demographic information. Participants will submit their completed survey to the CHW in a private church space, who will quickly assess for suicidality by examining responses to Question #9 of the PHQ-9. Eligibility for the Randomized Controlled Trial (RCT) depends on the participants' total PHQ-9 score:

- Participants whose PHQ-9 9 (negative depression screen), are ineligible for the RCT and will receive a copy of Mental Health Resources.

- Participants whose PHQ-9 10 (positive depression screen), will be eligible for the RCT and invited to sign informed consent to participate in the study.

Page 12 of 25

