Safety Assessment and Quality Assurance. If a subject responds positively to Question #9 of the PHQ-9 or verbally endorses suicidality, the CHW will immediately initiate a safety assessment protocol. The CHW will assess and quantify safety risk with the Columbia-Suicide Severity Rating Scale (C-SSRS). After administering the C-SSRS, the CHW will immediately call the on-call study clinician (Drs. [name] or [name] or another licensed clinician). The on-call clinician will then conduct a brief, standardized clinical interview that reviews the score on the C-SSRS and quantifies the specific suicidal plans and access to lethal means (e.g., firearms). For participants with active suicidal ideation or behavior with imminent risk of harm to self or others, severe disability, or psychosis, the CHW will immediately collaborate with church staff and the participant's family for transfer to a local Emergency Room or Mobile Crisis. For participants with non-active suicidal ideation/behavior, the CHW will inform the study PIs within 24 hours and complete the Stanley-Brown Safety Plan94,95 (see 'Safety Plan' in Appendix). The CHW will inquire to see if the subject is currently in treatment, and if so, he/she will attempt to contact the participant's mental health provider. The subject will be referred for an in-person clinical interview with the on-call study clinician within 48 hours. If the subject does not attend or refuses the in-person assessment, Mobile Crisis will be dispatched to the residence.

Eligibility for Participation in RCT among Participants with a Positive Depression Screen. Inclusion criteria are: 1) Adults 18 years and older; 2) English speaking; 3) PHQ-910. Exclusion criteria are reporting active suicidality, or verbally endorsing homicidal ideation or psychotic symptoms, and those actively receiving formal treatment for depression or mental health illness (e.g. with medications and/or psychotherapy).

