[] Abbreviated Submission - This information is included in an attached stand-alone protocol. Proceed to the next question

We expect the level of risk due to this intervention to be minimal as no invasive measures or procedures are proposed. However, given the target sample, patients may experience distress as they are asked questions about depressive symptoms and other assessments. It is possible that some patients may find the frequency of calls and visits to be excessive. There is a potential risk to the participant with regards to possible violation of the participant's privacy since survey responses will be used as a source of data. Two CHWs and at least one Project Coordinator (PC) will be present for each depression screening event at designated church study sites. The CHWs will focus on reviewing PHQ-9 scores with community members. The PC(s) will focus on consenting eligible adults who screen positive for the Randomized Controlled Trial. When the prospective participant has completed the PHQ-9, the CHW and PC will briefly calculate their total PHQ-9 score and assess for suicidality. Individuals who score 10 on the PHQ-9 will be contacted within 14 days to schedule a baseline assessment and verify study eligibility. A telephone interview assessment will then be scheduled for those who agree. At the start of this interview, the interviewer will obtain informed consent from the patient. The consent will include permission to contact the participant's treatment facility where they seek depression treatment, obtain selected data from the patients' other health care providers, and share information with our CUIMC collaborators. All participants will be informed that they can refuse to answer questions, stop the assessment at any time, or withdraw from the study if they so wish, without in any way affecting their eligibility or receipt of usual health or social services. Every effort will be made to streamline the interview and make it as comfortable as possible. Safety Assessment During Screening and Study Procedures. We have developed a comprehensive safety plan that will be activated if a research participant endorses suicidal ideation either verbally or on the PHQ-9 (included in IRB #6368). First, the CHW will screen for suicidality with the Columbia-Suicide Severity Rating Scale (C-SSRS). This measure to was designed to quantify the risk and intent of suicidal ideation / behavior. Second, the CHW will immediately contact the on-call clinician, who will conduct a standardized clinical assessment to evaluate immediacy of suicidal risk. If the research participant has active suicidal ideation/behavior, the on-call clinician will refer the participant to immediate clinical care by either calling 911 (if the patient consents for treatment) or Mobile Crisis (if the participant refuses to go to the emergency room). If the research participant does not have active suicidal ideation/behavior, the on-call clinician will refer the participant for an in-person clinical assessment with a licensed clinician on the research study team within 48 hours. If the participant

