
does show up or refuses the in-person clinical assessment, [name] will contact Mobile Crisis and have Mobile Crisis conduct a home safety assessment at the participant's home address.Protections Against Risk. The Multi-PIs will apply for a Certificate of Confidentiality. Confidentiality of patient information will be safeguarded in several ways. All research staff will be thoroughly trained in the need to maintain strict confidentiality. Data will be reported in aggregate form only. All participant-identifying information on paper will be kept in locked files accessible only to study staff. All electronic information will be password protected. No information obtained during the study will be used for any purpose other than the purpose for which the person has consented. The physical risks of the study procedures are minimal and the potential risks have been outlined above. The clinical care of any given participant will be handled entirely by the participant's primary care provider, unless emergency care is needed due to suicidality as outlined above, and study participants will be made aware of this at the baseline assessment. Similarly, any medical problem that arises during study visits will be referred to the participant's primary care provider. For those who do not have any provider, the PC will provide the participant with information to local health center.

Potential Benefits:

Provide information regarding any anticipated benefits of participating in this research. There should be a rational description of why such benefits are expected based on current knowledge. If there is unlikely to be direct benefit to participants/subjects, describe benefits to society. Please note that elements of participation such as compensation, access to medical care, receiving study results, etc. are not considered benefits of research participation.

[] Abbreviated Submission - This information is included in an attached stand-alone protocol. Proceed to the next question

We expect that community members in both arms of the study will benefit from SBIRT or RAU. All study enrollees will receive a modest gift card compensation for participation:

1. Clergy will recieve a \$100 gift card for completing semi-structured interviews.

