Data Safety Monitoring Plan. In compliance with NIH requirements, we will establish a data and safety monitoring plan (DSMP). The purpose of these plans is to ensure the safety of participants and the validity and integrity of the data. Considering the study rationale, population, procedures, and the risk: benefit profile as outlined; the overall risk level for participation in this screening intervention is classified as minimal. Due to the classification of this study as minimal risk, the following members of the investigative team will serve as the Data Safety Monitoring Committee and will perform the monitoring: [name], Contact-Principal Investigator (Columbia University, Dept. of Psychiatry). [name] will be responsible for corresponding with NIMH. In addition to providing timely reports to NIMH, regarding (i) Unanticipated problems or unexpected serious adverse events that may be related to the study protocol, (ii) IRB-approved revisions to the study protocol that indicate a change in risk for participants, and (iii) Notice of any actions taken by the IRB or regulatory bodies regarding the research and any responses to those actions, [name] will be responsible for: Reviewing all PHQ-9 questionnaires and assessments by participants students at baseline, 3-, and 6months; Reviewing safety plans documented by CHWs; and Reviewing rates of participant referral to treatment.[name], Multiple-Principal Investigator (Columbia University, Dept. of Neurology). [name] will provide site oversight by auditing CHW protocols and church sites where the intervention and control programs will take place. In addition to intervention fidelity monitoring, [name] will perform random interviews with CHWs (at least once at each church site) to evaluate the presence of any adverse reactions to the curriculum that may not be captured by questionnaire data. [name], Co-Investigator (Hebrew Home at Riverdale). [name] is the head project statistician at the Research Division of the Hebrew Home at Riverdale. She and her team will act as the Data Coordinating Center (DCC) and regularly review program data, which will be discussed with the MPIs monthly. These data will include guestionnaire items designed to capture adverse student emotional responses to the intervention. [name] has directed over 100 DCCs for single and multi-site projects, and has served on many DSMBs.Project Director – TBN. The Project Director will be present on site at every intervention and control program. In addition to project management activities such as recruitment, consenting, training, and data collection, the PD will be responsible for identifying and reporting any adverse encounters - related or unrelated to the intervention - to the Multi-PIs. These include adverse emotional responses, interpersonal conflicts, physical accidents or any other participant safety concerns that may occur during the intervention. Monitoring Study Safety: The data and safety monitoring plan will consist of reporting of adverse events to the IRB and to NIH trials. Adverse events will be reported to the Columbia IRB, which has the authority to halt the trial if it perceives that harm is occurring due to the intervention. Summaries of adverse events reports will be made to NIH in the yearly progress report and at the end of year 5, in the final report, unless the nature of a particular event is such that it bears reporting to NIH immediately. The progress of the trial will also be evaluated from the initial screening of participants by inclusion and exclusion criteria to the informed consent process to the provision of participant study instruction to staff training in Good Clinical Practices (GCP) and regulations pertaining to the Conduct of Human Participant Research. This will also include internal monthly quality control audits, periodic assessments of data quality and timeliness,

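### The immediate on-call clinician call starts only on suicidality, so voiced homicidal ideation without suicidality, itself a trial exclusion, has no prescribed immediate clinician contact

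*Protocol*

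**What the plan says.** Under Safety Assessment and Quality Assurance, the trigger is: "If a subject responds positively to Question #9 of the PHQ-9 or verbally endorses suicidality, the CHW will immediately initiate a safety assessment protocol". The community health worker (CHW) gives the C-SSRS, and then: "After administering the C-SSRS, the CHW will immediately call the on-call study clinician". The emergency branch of the same paragraph covers active suicidal ideation or behavior with "imminent risk of harm to self or others, severe disability, or psychosis" and leads to transfer to an emergency room or Mobile Crisis.

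The next paragraph, on eligibility for the randomized trial, says: "Exclusion criteria are reporting active suicidality, or verbally endorsing homicidal ideation or psychotic symptoms". It gives no step to take when such a statement is heard.

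Potential Risks describes a safety plan, held in another IRB protocol, that is activated "if a research participant endorses suicidal ideation either verbally or on the PHQ-9". The C-SSRS comes first there and the clinician contact second. Protections Against Risk leaves clinical care to the participant's own primary care provider "unless emergency care is needed due to suicidality as outlined above".

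Data and Safety Monitoring adds a general duty: "the PD will be responsible for identifying and reporting any adverse encounters". These reports go to the Multi-PIs.

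**The concern.** The protocol foresees the presentation. Homicidal ideation is a named exclusion, and the emergency branch speaks of harm to others. But the only route to an immediate clinician contact begins with suicidality and passes through a suicide scale.

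The CHWs are lay workers and will follow the written steps. Under those steps, any positive answer to Question 9, even without active intent, brings an immediate clinician call. For non-active cases it also brings notice to the principal investigators within 24 hours, referral for an in-person interview within 48 hours, and Mobile Crisis if the person refuses or does not attend. A person who voices a wish to kill someone else and denies suicidality triggers none of these. The judgment about imminence, which belongs with a clinician, would be left to the CHW. What is at stake is the safety of participants and third parties.

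**Working it through.** The protocol states no figure on this point, so the check is a reading of every place that could prescribe an immediate clinician contact for homicidal ideation without suicidality.

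| Protocol location | What starts it | What follows | Immediate clinician contact for this case? |
|---|---|---|---|
| Safety Assessment and Quality Assurance, trigger | Positive Question 9 or voiced suicidality | C-SSRS, then immediate clinician call | No; not triggered |
| Same paragraph, emergency branch | Active suicidal ideation or behavior with imminent risk, including to others | Transfer to emergency room or Mobile Crisis | No; ideation toward others is not named, and the branch follows the suicidality trigger |
| Eligibility for the trial | Voiced homicidal ideation | Exclusion | No action stated |
| Potential Risks, safety plan | Suicidal ideation, voiced or on the PHQ-9 | C-SSRS, then immediate clinician contact | No; not triggered |
| Consent waiver, fourth criterion | Having been screened | Score and access to referral resources, enrolled or not | No |
| Protections Against Risk | A medical problem at a study visit | Primary care referral, or local health center information | No; and it is arguable whether this is a medical problem |
| Data and Safety Monitoring | Adverse encounters and safety concerns during the intervention | Project Director report to the Multi-PIs, no time limit | No |

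Every stated trigger of the immediate call is suicidality. Homicidal ideation appears once, as an exclusion.

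The number of contacts at which such a statement could be heard follows from the protocol:

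- Screening: 30 churches × 100 adults = 3,000 people. All of them count, since "There are no exclusion criteria for general depression screening". Expected positive screens are 3,000 × 20% = 600, and negative screens 3,000 − 600 = 2,400.
- Motivational interviewing: with an even split, 600 / 2 = 300 SBIRT participants × 6 sessions = 1,800 sessions at most. The first two are in person, so up to 300 × (6 − 2) = 1,200 may be by phone.
- Assessments: 600 × 3 waves = 1,800 at most, with the baseline wave by telephone.

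The documents give no disclosure rate. The screening survey described contains only the PHQ-9 and demographics, so disclosure there would be mostly unprompted. Purely as assumptions, 0.01%, 0.1% and 1% of those screened give 3,000 × 0.0001 = 0.3, 3,000 × 0.001 = 3 and 3,000 × 0.01 = 30 people. These cover screening only. Follow-up contacts would add to them by an amount the documents do not allow one to estimate.

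**The case against.** The strongest reply is that the protocol is not silent about such a person, and that part of the plan is not on view.

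- *There are other routes.* This stands. A reader might infer that voiced homicidal ideation leads to nothing, or at most to an untimed report. The table shows otherwise: resources are offered, a primary care referral is possible, and the Project Director must report. But none of these is an immediate clinician contact.
- *Phone sessions are covered.* This also stands in part. One might infer that phone sessions fall outside the reporting duty because the Project Director is on site only at programs. The duty extends to safety concerns during the intervention, and the phone sessions are part of the intervention. Physical presence is lacking by phone; the reporting route is not.
- *The emergency branch already covers psychosis and severe disability.* It may. The list can be read as three separate grounds for transfer, or as qualifiers of active suicidality. A reader might infer that these two conditions are uncovered, but the text supports only an ambiguity. The harm-to-others wording helps less: even on a generous reading it reaches behavior with imminent risk, not voiced ideation.
- *The full safety plan and the booster curriculum are not shown.* True, and either might contain a wider rule. But Potential Risks itself states what activates that plan, and it is suicidal ideation. A wider rule elsewhere would not match the protocol's own text.
- *An exclusion criterion need not carry a crisis procedure.* Fair as a general rule. Here, though, the same section writes a detailed procedure with a trigger that omits a danger the next paragraph names, so the trigger is drawn too narrowly.

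**Conclusion.** The point holds in a limited form. Both statements of the safety trigger are confined to suicidality, the clinician call follows the C-SSRS, and homicidal ideation without suicidality therefore has no prescribed immediate clinician contact, although the protocol expects staff to hear it. For psychosis and severe disability there is only a wording ambiguity.

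Two cautions on reading. The risk section's trigger is suicidal ideation endorsed aloud or on the PHQ-9; it should not be taken to mean a PHQ-9 total above the depression cut-off. And the point does not bear on power, sample size, the endpoint or the analysis; no statistical figure changes.

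The size cannot be estimated from the documents. Cases are probably few, and the 0.3 to 30 at screening rests wholly on assumed rates. The case for the change is that it is cheap and that a single missed case could be serious. The conclusion assumes that the text shown is what CHWs will follow and that the unseen plan is activated as Potential Risks says.

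**What to change.** - In the trigger sentences of Safety Assessment and Quality Assurance and of Potential Risks, add verbally endorsed homicidal ideation, at screening or at any later study contact, including phone sessions, telephone assessments and Zoom. The action is a direct call to the on-call clinician without the C-SSRS first.
- State that the clinician decides on emergency transfer.
- In Protections Against Risk, widen the emergency-care exception beyond suicidality to match.
- Optionally, punctuate the emergency list so that psychosis and severe disability clearly stand alone as grounds for transfer.

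The cost is about one sentence in each of the three places, one line in the CHW booster training, and a small number of extra calls to a clinician who is already on call. Those calls would arise in follow-up as well as at screening, and the documents give no rate from which to count them. Existing eligibility rules, the endpoint and the analysis stay as they are.

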(3) Community Members (n=600): CHWs, Project Coordinators, and Research Assistants will be present at church study sites to obtain written consent from eligible adults who screen positive for depression (PHQ-9 greater than 10). Consent procedures will occur in a private area of the church to protect patient confidentiality

[] Informed consent will be obtained but a waiver of written documentation of consent (i.e., agreement to participate in the research without a signature on a consent document) is requested.

Page 15 of 25

[x] A waiver of some or all elements of informed consent (45 CFR 46.116) is requested.

Waiver of consent is applicable to:

A portion of the study or subject population

Identify the portion of the study (e.g., retrospective chart review portion of the study) or subject population where a waiver of consent applies:

We request a waiver of consent for depression screening procedures with the PHQ-9

Select the applicable situation:

[x]This study qualifies for a waiver or alteration of consent as the following criteria are met in this study (provide justification for EACH of these criteria):

(1)The research involves no more than minimal risk to the subjects Provide justification:

The PHQ-9 is a widely used, brief, self report measure that takes approximately 3 to 5 minutes to complete. We received waiver of consent on NYSPI IRB #6368 to conduct church-based depression screening with the PHQ-9.

(2) The waiver or alteration will not adversely affect the rights and welfare of the subjects Provide justification:

The PHQ-9 is a screening measure and will not impact the welfare of subjects. If a patient expresses suicidal ideation on the PHQ-9, we will follow the Safety Procedures outlined in the previous section and initiate more in-depth assessment of suicidality with the Columbia-Suicide Severity Rating Scale

(3) The research could not practicably be carried out without the waiver or alteration Provide justification:

It would be impractical and overly time consuming to try to obtain consent prior to screening with the PHQ-9. Only adults with a positive depression screen (PHQ-9 greater than 10), will be eligible for the RCT and will be required to provide informed consent to participate in the RCT

(4) Whenever appropriate, the subjects will be provided with additional pertinent information after participation

Provide justification:

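### The protocol's two accounts of the suicide-risk procedure give opposite attendance conditions for contacting Mobile Crisis after the 48-hour referral

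*Protocol*

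**What the plan says.** The procedure appears first under Procedures, in the paragraph headed Safety Assessment and Quality Assurance. It appears again under Risks, Benefits & Monitoring, in the Potential Risks field, as Safety Assessment During Screening and Study Procedures.

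**Procedures.** The lower-risk branch opens: "For participants with non-active suicidal ideation/behavior, the CHW will inform the study PIs within 24 hours". The subject is then referred for an in-person interview with the on-call study clinician within 48 hours. The step ends: "If the subject does not attend or refuses the in-person assessment, Mobile Crisis will be dispatched to the residence".

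**Potential Risks.** The corresponding branch opens: "If the research participant does not have active suicidal ideation/behavior, the on-call clinician will refer the participant for an in-person clinical assessment", again within 48 hours. Mobile Crisis is then to be contacted for a home safety assessment if the participant "does show up or refuses the in-person clinical assessment".

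The Potential Risks text also cites a comprehensive safety plan held under IRB #6368, which is not among the documents available. The Procedures section answers No when asked whether an external protocol describes all procedures in the study.

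**The concern.** Both sentences govern the same people at the same step: those who endorsed suicidality, were judged not to have active ideation or behavior, and were referred to be seen within 48 hours. One account makes non-attendance a trigger for Mobile Crisis. The other, read literally, makes attendance the trigger.

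What is at stake is participant safety and the coherence of an IRB submission. Someone working only from the Potential Risks text would find no instruction for a participant who does not come and has not refused. The same text would have them contact Mobile Crisis for a participant who did come. The procedure starts at screening, where the target enrollment is 3,000.

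**Working it through.** No arithmetic applies. The check is whether the two sentences concern the same step and whether their conditions can both be true.

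**1. Same branch.** Procedures addresses non-active ideation or behavior. Potential Risks addresses participants without active ideation or behavior. These are the same group.

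**2. Same preceding step.** Both refer the participant for an in-person assessment by a study clinician within 48 hours.

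**3. Same consequence.** Procedures dispatches Mobile Crisis to the residence. Potential Risks has Mobile Crisis make a safety assessment at the home address. For this comparison they are equivalent.

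**4. The condition.** Taking each sentence exactly as written:

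| What happens after the referral | Procedures | Potential Risks |
|---|---|---|
| Participant refuses | Mobile Crisis | Mobile Crisis |
| Participant misses it without refusing | Mobile Crisis | No action stated |
| Participant attends | Not triggered | Mobile Crisis |

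The second and third rows are not two separate faults. Reversing one condition flips both complementary cases, so there is one discrepancy, in the attendance condition.

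**5. Does anything else in the protocol resolve it?** No. The plan under IRB #6368 is cited but not shown, and the protocol itself says that no external document covers all its procedures. The consent-waiver justification says "we will follow the Safety Procedures outlined in the previous section and initiate more in-depth assessment of suicidality", but this only points to a safety text and does not restate the trigger.

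**The case against.** **It is a typing slip.** This is the strongest reply, and most of it stands. The Potential Risks sentence pairs attendance with refusal and ends in a home visit, which is an odd response to someone a study clinician has just seen. The same text contains other slips of grammar. A reader with both sections in hand would probably not be misled. So a reader might infer two deliberately different procedures, but the documents do not support that. What survives is that the sentence is a rule for handling suicide risk, not background, and as written it contradicts its counterpart.

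**The word may have been lost in extraction from the PDF.** This cannot be excluded: the sentence may cross a page boundary, and inequality signs are missing elsewhere, for example in the PHQ-9 cut-off. However, the disputed words run unbroken, and losing a whole plain word is less likely than losing a symbol. The PDF page would settle it.

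**The accounts also differ on the threshold for emergency care.** A reader might infer a second contradiction. Procedures has "For participants with active suicidal ideation or behavior with imminent risk of harm to self or others, severe disability, or psychosis", while Potential Risks has "If the research participant has active suicidal ideation/behavior, the on-call clinician will refer the participant to immediate clinical care by either calling 911". If the imminent-risk phrase restricts the first, active ideation without imminent risk has no clear branch there. But the phrase can equally be read as describing active ideation. Both accounts also send every case through the C-SSRS and the on-call clinician, and in Potential Risks it is that clinician "who will conduct a standardized clinical assessment to evaluate immediacy of suicidal risk". The documents do not establish a contradiction here.

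**Other sections rely on the conflicting texts.** A reader might infer that the consent waiver, or what participants are told at baseline, rests on the reversed wording. The waiver's reference points most naturally to the Procedures account, which does not have it. The reference under Protections Against Risk concerns emergency care for suicidality, not the attendance step after a non-emergency referral. Neither inference is supported.

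**Conclusion.** The point holds as an internal inconsistency: the two accounts state opposite attendance conditions for the same step, and the Potential Risks account leaves a missed assessment without refusal uncovered. It is limited to that one condition. Confidence is high that the texts conflict as written, subject to the PDF carrying the same words. It is probable, not proven, that a word was dropped.

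The number of participants affected cannot be derived, because the documents give no rate for endorsed suicidality or for missed assessments, and none is assumed. The treatment-engagement outcome, the secondary outcomes, the sample size and the analysis are untouched. The correction should be made because the sentence governs a safety response and costs almost nothing to put right. The conclusion covers only the two texts in this protocol and says nothing about what the plan under IRB #6368 contains.

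**What to change.** Reconcile Safety Assessment and Quality Assurance (Procedures) with Safety Assessment During Screening and Study Procedures (Potential Risks), so that both state the same attendance trigger and a participant who misses the assessment without refusing is expressly covered. The investigators decide the clinical content of that trigger.

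Check any CHW training material or safety-plan text that carries the same wording, including the plan cited under IRB #6368. While amending, the investigators may also confirm that both accounts intend the same active/non-active threshold, as a clarification rather than the correction of an established error.

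The cost is a wording amendment, plus an edit to training material only if it repeats the sentence. No procedure, visit or data collection is added, and the two sections need no restructuring.
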